APPENDIX I: VULNERABLE POPULATIONS

I. N/A

II. Cognitively or decisionally impaired individuals: N/A

III. Children: N/A

IV. Pregnant women: N/A

V. Prisoners: N/A

VI. Students and/or Employees:

A. N/A

B. N/A

C. N/A

Appendix III: Data collection From Chart Review

Age at time of surgery:

Gender:

Race:

Total Burn TBSA:

Deep partial thickness/ full thickness burn percentage:

Time to first opioid from minutes post-op following completion of post-operative recovery period:

First opioid dose:

First opioid route:

Total opioid administered in morphine equivalents for 72 hours post-operatively:

Non-opioid adjunct medication administration:

Anesthesia occurrences in first 72 hours post-op:

Time of donor site dressing open to air:

Time of first donor site dressing change:

[figure not shown]
Prior to admission opioid use:

Donor site size:

Donor site location:

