To provide analgesia while reducing the use of opioids and their associated adverse effects, there are multiple distinct approaches to postoperative donor site pain control. Such methods including continuous subcutaneous local anesthetic, subcutaneous anesthetic injections, topical agents, wound dressings, and nonpharmacological strategies.² Based on a review performed by Sinha et al.², few evidenced based recommendations exist despite the significance of donor site pain in this patient population. Within the category of subcutaneous anesthetic injections, the most robust evidence supports the use of lidocaine with 1:500,000 epinephrine based on a randomized control trial conducted by Gacto et al.⁵ Other common agents used include ropivacaine and bupivacaine, but further studies are needed to make true evidence-based recommendations for their use. Additionally, while these traditional formulations may provide effective analgesia at the donor site, the duration of action is relatively short, lasting 12 hours or less.³

Liposomal bupivacaine (Exparel) is a prolonged release formulation that can extend the duration of donor site analgesia. According to Dissanaike et al.³, Exparel has been shown to provide postsurgical analgesia for up to 72 hours and reduce postsurgical opioid requirements when compared with Bupivacaine or placebo in multiple surgical settings. In the setting of STSG donor site pain, however, Exparel use has not been extensively described. We hypothesize that the use of Exparel at STSG donor sites will improve pain control compared to the current standard of care of lidocaine.

2. We hypothesize that use of liposomal bupivacaine (Exparel) will decrease post-operative pain at the donor site compared to the current standard of care, lidocaine, for split thickness skin grafting in patients with burn injuries. We have two specific aims.

- a. To identify whether pain is decreased in patients receiving Exparel injections post-operatively at STSG donor sites compared to patients receiving lidocaine injections as measured by pain scores.
- b. To determine if there is a reduction in post-operative opioid pain medication consumption in STSG patients receiving Exparel injections at the donor site compared to patients receiving lidocaine injections.

B. Background and Significance

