3. We anticipate a reduction in pain scores by 2 points with SD 2.5 in the experimental group. Power analysis for 80% power yields 25 patients per group. We will aim to enroll a total of 50 patients, 25 in each group.

D. Subject Criteria (See Vulnerable Populations appendix, if applicable):

1. Inclusion criteria: State the criteria for inclusion in the study in a specific and detailed manner.
 - E. Age \geq 18 years, English or Spanish speaking, Burn injury with the following parameters: $\leq 20\%$ TBSA partial thickness, $\leq 5\%$ TBSA deep partial or full thickness, first skin autografting procedure for hospitalization, donor site anterior or lateral thigh
2. Exclusion criteria: State the criteria for excluding potential subjects from the study in a specific and detailed manner.
 - E. Chronic pain syndrome on opioid pain medications at baseline, $>20\%$ TBSA partial thickness burn, $>5\%$ TBSA surgical area of burn injury (deep partial or full thickness injury), pregnant women, age < 18 , not first skin autografting procedure during hospitalization, allergy to lidocaine or other local anesthetics, burns to anterior thighs, inability to give informed consent
3. Withdrawal/Termination criteria: Include the specific circumstances in which the subject's participation will be terminated by the investigator. Include any necessary safety precautions to be applied to those who withdraw (tapering drug doses, evaluative x-ray, etc.)
 - E. Serious adverse reactions to lidocaine or liposomal bupivacaine including cardiac event, arrhythmia, seizure, anaphylaxis, and loss of limb. Subjects who experience these reactions will be medically stabilized and undergo standard work-up based upon symptoms. The subject will be unblinded and the medication administered will be documented in their medical record as an allergy. They will be withdrawn from the study and the adverse reaction will be reported to the IRB within 24 hours.
4. Clarify whether a study subject may participate in another research study while participating in this research study.
 - E. Subjects may participate in additional research studies as long as study protocols do not interfere with one another. For example, subjects may not be enrolled in a study comparing experimental pain management or alternative methods of skin autograft harvest.

E. Specific methods and techniques used throughout the study

1. Laboratory tests: No laboratory specimens will be required for participation in this study.

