2. Study Procedures:
 - a. Enrolled subjects will be randomized to the control group or the experimental group. Preoperatively, subjects will complete a validated visual analog pain assessment scale to assess baseline pain levels. This is described in further detail below. Informed consent for study participation will be obtained by a team member preoperatively and informed consent for split thickness autografting will be obtained by a surgical team member. All questions will be answered and risk/benefits/alternatives will be explained in detail to the study subject. The subject will then be taken back to the operating room and anesthesia will be induced. The surgical timeout will occur verifying subject name, medical record number, planned operation, and surgical site. The subject will be prepped and draped in a sterile manner.
 - b. For the control group: The recipient burn site will be excised to healthy, bleeding tissue and the size of the defect will be measured. The anterior thigh will be marked to determine the size of the autograft. Tumescent solution with lidocaine and epinephrine will be injected using a needle or cannula at the donor site. A split thickness skin graft will be taken using a Zimmer dermatome. The skin graft will be applied to the recipient site and will be fixated in the standard fashion. The donor site and recipient site will then be dressed according to the preference of the attending physician. The patient will then awaken from anesthesia. This procedure will typically take between 60 to 120 minutes.
 - c. For the experimental group: The procedure described above will be identical to that performed to the control group with the following exceptions: Liposomal bupivacaine with plain bupivacaine diluted according to manufacturer recommendations will be infiltrated subcutaneously at the skin graft donor site prior to conclusion of the procedure. The procedure length will be unaffected.

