 - d. Post-operatively, subjects will recover from anesthesia. Once the subject returns to routine care following completion of recovery from surgery, time to first opioid medication will be recorded. The Visual Analog Pain scale will be used to assess donor site pain at set time intervals. This will occur for three total days. The scale will take approximately one minute to complete and is easily completed by non-English speaking subjects as it is a visual scale. Daily narcotic usage will be obtained from the medical record and will be measured in morphine equivalents. Length of stay will be evaluated from the medical record.
3. Harvesting of the split thickness autograft will be performed in the standard fashion as described above. Treatment of partial and full thickness burns with autografting is the standard of care for many patients with burn injuries. Postoperatively and preoperatively, patients will complete a validated pain assessment scale on a daily basis. Pain is routinely assessed as part of postoperative care and nursing management of patients. As part of the study, a pain scale will be used to specifically ask about pain related to the STSG donor site, whereas the pain scale is typically used to ask about global pain in patient care.
4. Split thickness autografts will be harvested from the anterior and lateral thigh of subjects. Harvested skin may be greater than the size of the recipient burn site. Excess skin will be disposed of. No tissue samples will be collected as part of this study.
5. Timeline:

F. Risk/benefit assessment:

1. Physical risk: Risks include potential adverse reaction to liposomal bupivacaine (Exparel) or lidocaine. Adverse reactions associated with liposomal bupivacaine have been shown to be equal in severity and frequency to those expected with the routine use of lidocaine according to the FDA approval for liposomal bupivacaine. Patients in both groups will be undergoing split thickness skin grafting and will be at risk for common surgical post-operative events, including bleeding, infection, and pain.

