- **Not Related** – An event is considered to be not related to the use of the test article when the event is DEFINITELY UNRELATED or UNLIKELY to have any relationship to the use of the test article.
- **Related** – An event is considered to be related to the use of the test article when there is a POSSIBLE, PROBABLE, or DEFINITE relationship between the adverse event and the use of the test article.

For example, a single occurrence of an event that is uncommon and known to be strongly associated with drug exposure (e.g., seizure, cardiac arrhythmia) has a reasonable possibility of association with the test article. One or more occurrences of an event that is not commonly associated with drug exposure, but is otherwise uncommon in the population exposed to the test article, may have a reasonable possibility of association. Adverse events which are known to be common in the population under study would require additional evidence (e.g., strong temporal relationship, recurrence on re-challenge, unusual severity, and/or increasing frequency) before being considered possibly related.

Adverse events which are known to occur frequently in the population defined by this protocol include: wound infection, pain and itch of the wound, and contact dermatitis.

- d. Follow-up of Subjects with Adverse Events: For subjects who are experiencing ongoing unresolved adverse events at the time of their study completion or early discontinuation from the study, appropriate follow-up visits in order to determine the outcome of the event will be scheduled.
3. Subjects who experience an adverse events will be medically stabilized and undergo standard work-up based upon symptoms. The subject will be unblinded and the medication administered will be documented in their medical record as an allergy. They will be withdrawn from the study and the adverse reaction will be reported to the IRB within 24 hours as per procedure outlined above.

III. Subject Participation

A. Recruitment:

1. Patients will primarily be recruited in the KU Hospital Burn Unit. Rarely, patients may be recruited prior to their admission to the Burn Unit in either the KU Emergency Department or KU Burn and Wound Clinic prior to proceeding to the operating room. No recruitment will take place at locations outside of KUMC.

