7. N/A
8. N/A

B. Sample / Specimen Collection: N/A

C. Tissue Banking Considerations: N/A

D. Procedures to protect subject confidentiality: Patients will be identified by nursing staff as enrolled in the study to collect the post-operative pain scale assessments. Nursing staff are experienced in maintaining patient confidentiality as this is an expectation with all levels of care they provide. Following the data collection process, the study subjects will be deidentified to maintain their confidentiality.

E. Quality Assurance / Monitoring

1. Data that is collected will be self-reported from patients or collected as objective data from the medical record. No subjective assessments will be done by study team members. There is a chance that study subjects could intentionally falsify their pain scores for secondary gain, for example, to receive more narcotic pain medications. To limit this potential, we will not be including patients in the study who have ongoing opioid use for chronic pain or abuse prior to admission.
2. There are no plans for third party monitoring of this study.

V. Data Analysis and Reporting

- A. Statistical and Data Analysis:** Differences between groups will be assessed using Chi square test for categorical variables and Student's t test for two means. Confidence intervals will be calculated to 95% and a p value of less than 0.05 will be considered statistically significant. Final statistical analysis will be conducted by statistician. Interim analysis is planned for at the half way point of the study (20 patients completed). Interim statistically analysis will be conducted by Co-Investigators.
- B. Outcome:** We expect that the experimental group will have decreased pain scores compared to the control group. We estimate a 2 point difference in pain scores for the STSG donor site and that this difference will occur at 1, 2 and 3 days post-op. We expect that opioid consumption and time to first opioid dose will also be decreased in the study group. Our power analysis calculation based on pain score decrease aims to enroll 40 patients in the study and this is our anticipated study end point.
- C. Study results to participants:** Study subjects may submit a written request to receive study results after completion of the study. If requested, results will be mailed to the study subject after completion of data analysis.

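### Aim b compares total post-operative opioid use with no record of opioid given in hospital before grafting; collecting it and adjusting for it would be a cheap gain in precision

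*Combined protocol and SAP*

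**What the plan says.** Section I.A.2 gives the second aim: "To determine if there is a reduction in post-operative opioid pain medication consumption in STSG patients receiving Exparel injections at the donor site", against lidocaine. Two places define what is collected. Section II.E.2.d states that "Daily narcotic usage will be obtained from the medical record and will be measured in morphine equivalents", and Appendix III lists "Total opioid administered in morphine equivalents for 72 hours post-operatively". Neither limits the count by source of pain.

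Before surgery, pain is measured but opioid use is not. Section II.E.2.a states: "Preoperatively, subjects will complete a validated visual analog pain assessment scale to assess baseline pain levels". The only item on earlier opioid use in the visible Appendix III is "Prior to admission opioid use". Eligibility looks at the same period: section II.D.2 excludes "Chronic pain syndrome on opioid pain medications at baseline", and section IV.E.1 adds that "we will not be including patients in the study who have ongoing opioid use for chronic pain or abuse prior to admission". Opioid given between admission and grafting is neither collected nor a reason for exclusion.

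On setting, section III.A.1 states: "Patients will primarily be recruited in the KU Hospital Burn Unit". On analysis, sections II.C.1 and V.A specify a t test for means and name no covariate. The planned size is 50 in section II.C.3 and 40 in section V.B.

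**The concern.** A patient in a burn unit awaiting a graft may already be receiving opioid for the burn. If so, what that patient received just before surgery should help predict the 72 hours after it. The plan does not record this amount. It records use before admission, and the exclusions probably leave that field with little variation.

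Two things follow for aim b. Differences between patients that were already present before surgery stay in the error term of the t test. And if the arms happen to differ in pre-operative use, nobody can see it or adjust for it afterwards. With 20 to 25 patients per arm and no power calculation for opioid use, precision that is cheap to obtain is worth having.

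**Working it through.** **1. The plan's own figure.** Section II.C.3 assumes a 2-point difference, SD 2.5 and 80% power. Two-sided 0.05 is assumed, because the plan does not state sidedness.

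n per group = 2 × (1.960 + 0.842)² × (2.5 / 2)² = 2 × 7.85 × 1.5625 = 24.5, so 25.

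The stated 25 per group is reproduced. It applies to the pain score only. The documents give no mean, SD, effect size or baseline correlation for opioid use, so everything below rests on assumptions.

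**2. What adjustment would gain.** Let r be the correlation between morphine equivalents in the 24 h before surgery and the 72-hour total after it. Adjustment leaves a fraction 1 − r² of the outcome variance, which is equivalent to multiplying the sample by 1/(1 − r²). For illustration only, take an opioid difference of 0.5 SD. Then power ≈ Φ(0.5 / √(1 − r²) × √(n/2) − 1.96).

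| r (assumed) | Variance left, 1 − r² | Sample multiplier | Power, 20 per arm | Power, 25 per arm |
|---|---|---|---|---|
| 0 | 1.00 | 1.00 | 35% | 42% |
| 0.2 | 0.96 | 1.04 | 36% | 44% |
| 0.3 | 0.91 | 1.10 | 38% | 46% |
| 0.5 | 0.75 | 1.33 | 45% | 53% |
| 0.7 | 0.51 | 1.96 | 60% | 70% |

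Example for r = 0.5 and 25 per arm: 0.5 / √0.75 = 0.577; 0.577 × √12.5 = 2.04; Φ(2.04 − 1.96) = 53%.

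These figures ignore the small cost of estimating the covariate coefficients. At r = 0.2 the net gain would therefore be close to nil.

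**3. Chance imbalance.** In SD units, the difference between arms in any baseline variable has standard error √(2/n).

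- 25 per arm: √(2/25) = 0.283. A gap above 0.5 SD has probability 2 × [1 − Φ(0.5 / 0.283)] = 8%.
- 20 per arm: √(2/20) = 0.316, and the probability is 11%.

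A gap of 0.5 SD in pre-operative use moves the unadjusted opioid difference by r × 0.5 SD: 0.10 SD at r = 0.2 and 0.35 SD at r = 0.7.

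**4. What is already collected.** Appendix III has total burn area, deep-burn percentage, donor-site size and non-opioid adjuncts, and there is a pre-operative pain score. Burn size and baseline pain are related to opioid need, but none of these records the opioid dose itself.

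**The case against.** The strongest objection is that total opioid use is the right quantity for aim b. Sections I.B.1 and I.C.2 justify the trial partly by the systemic harms of opioids, and those follow total exposure whatever pain the drug was given for. Specificity to the donor site is handled by the pain scale (section II.E.3 and Appendix IV). This stands. A reader might infer that a local drug is being judged by the wrong outcome, but the documents' rationale does not support that.

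The second objection is that allocation is randomised 1:1, and the t test's type I error already allows for chance imbalance in any covariate, measured or not. This also stands. A reader might infer that an imbalance would bias the result or pass as a drug effect. What remains is lost precision and no means of adjusting the particular sample obtained.

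Third, the documents do not show that opioid given for burn pain dominates the 72-hour total. They give no breakdown by pain source, no time from admission to surgery and no mention of standing orders. Eligibility also limits burn size and requires a first graft. The stronger statement is therefore unsupported, and the gain may be small.

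Fourth, a reader might go on to redefine time to first opioid as time to the first as-needed dose. Appendix III does not separate scheduled from as-needed doses, so a scheduled dose could set that time. But orders after surgery are written after randomisation, and only subjects are blinded (section II.C.2), so the redefinition could introduce bias of its own.

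Finally, absence can be judged only on the text available. A figure is not shown just above the prior-use field in Appendix III, and some text before that appendix is unavailable. No visible section mentions a pre-operative in-hospital opioid field.

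**Conclusion.** The point holds as an inexpensive improvement to aim b. It does not make the planned comparison invalid. On the visible text, the plan has no measure of opioid given in hospital before grafting, and its one opioid baseline is likely to be uninformative.

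The size of the gain is unknown. It runs from almost nothing at r = 0.2 to the equivalent of nearly doubling the sample at r = 0.7, and the documents do not say where in that range this population lies. The conclusion rests on two assumptions: that a fair share of subjects receive opioid in hospital before grafting, and that this predicts later use. If few do, little is gained, and little is lost beyond the abstraction time.

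**What to change.** 1. In Appendix III, add total opioid in morphine equivalents given in the 24 h before surgery, taken from the same medical record. The window closes before the study injection, so the drug cannot affect it.
2. Add a flag for subjects with less than 24 h of record. Leave the amount blank where there is no record; do not enter it as zero use. In the model, a blank can be filled with the mean of the recorded values over both arms, with the flag kept as a covariate.
3. In section V.A, state before any outcome data are examined that the 72-hour post-operative total will be compared by ANCOVA with treatment group, the pre-operative amount and the flag. Report the estimated difference with its 95% confidence interval.
4. Optionally, record whether the first post-operative opioid was scheduled or as needed, for description or a sensitivity analysis only. Keep the present definition of time to first opioid.

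The cost is one amount and one flag per subject from a chart already under review, and a sentence in section V.A. The drawbacks are abstraction time and incomplete prior records for same-day admissions. Clinical care is unchanged.

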Appendix IV: Pain Assessment Scale

Please circle the intensity of your pain level at your **donor site** at this moment

Subject Initials: _____

Time Completed: _____

Date Completed: _____

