Liposomal Bupivacaine Versus Lidocaine for Skin Graft Donor Site Pain

NCT03854344

13 Nov 2018

Version date: 11/13/18

Principal Investigator: [name]

Study Title: Prospective Study of Liposomal Bupivacaine for Pain Control of Split Thickness Skin Graft Donor Sites

Co- Investigator(s): [name]; [name]; [name]; [name], [name], BSN

I. Purpose, Background and Rationale

A. Aim and Hypotheses

1. Split-thickness skin grafts (STSG) play an integral role in the treatment of burn, traumatic, and chronic wounds.¹ Over 160,000 skin grafts are performed annually and are used to treat one of every three burn injuries.¹ During the procedure, a graft is taken from a remote area of healthy skin, commonly the proximal thigh, and transferred to the burn wound. Following STSG harvest, a wound remains at the donor site that will heal by re-epithelialization over the coming weeks.¹ Common complications of the donor site wound include excessive pain, impaired healing, and scarring.² In many cases, the donor site is more painful than the recipient site, and has been reported by patients to be one of the most distressing symptoms in the early postoperative period.² Opioids are a mainstay of treatment of post-surgical pain due to their potent analgesic effects.³ Opioid may be associated with adverse effects such as nausea, vomiting, constipation, urinary retention, and most seriously, respiratory depression.⁴ Chronic opioid use may also induce tolerance and result in hyperalgesia.³

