3. N/A

II. Research Plan and Design

- A. Study Objectives:** The objective of this study is to determine if use of liposomal bupivacaine (Exparel) decreases postoperative pain at the donor site compared to lidocaine for split thickness skin grafting in patients with burn injuries. In addition, we aim to identify if use of Exparel at the donor site for split thickness autografting decreases opioid pain medication consumption postoperatively compared to use of lidocaine at the donor site in patients with burn injuries.
- B. Study Type and Design:** This study will be a prospective, randomized controlled trial. Study subjects will be blinded to their randomization to avoid bias. The control group will undergo split thickness autografting using the standard protocol, involving injection of lidocaine with epinephrine at the donor site. The experimental group will undergo injection of liposomal bupivacaine (Exparel) at the time of harvest of the skin graft. Baseline pain levels will be obtained for all subjects using a validated pain assessment scale, the

Visual Analog Pain Scale. Postoperatively, time to first opioid pain medication (excluding immediate postoperative recovery from anesthesia), total opioid consumption on a daily basis, and donor site interval pain scores using a validated pain assessment scale will be obtained. The experimental group will then be compared to the control group to determine if there is a significant difference in pain levels, time to first opioid, and overall opioid consumption between the two groups.

C. Sample size, statistical methods, and power calculation

[figure not shown]
1. Patients will be randomized using a computerized random number generator with 1:1 randomization. Differences between groups will be assessed using Chi square test for categorical variables and Student's t test for two means. Confidence intervals will be calculated to 95% and a p value of less than 0.05 will be considered statistically significant.
2. Only subjects will be blinded to their randomization group. Study subject number will be linked to their randomization group. Blinding may be broken if the subject experiences an adverse reaction to the medication utilized for their group so that they are aware that they cannot receive the medication in the future.

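### The pre-operative pain score has no stated body site and no role in the analysis; if taken on the donor-site form, it will probably carry little information

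*Combined protocol and SAP*

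**What the plan says.** Section II.B plans a baseline for everyone: "Baseline pain levels will be obtained for all subjects using a validated pain assessment scale, the" Visual Analog Pain Scale. II.E.2.a fixes the timing: "Preoperatively, subjects will complete a validated visual analog pain assessment scale to assess baseline pain levels". Neither section names a body site.

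II.E.3 takes the two periods together, "Postoperatively and preoperatively, patients will complete a validated pain assessment scale on a daily basis", and after one sentence on routine nursing assessment adds that "a pain scale will be used to specifically ask about pain related to the STSG donor site", in contrast to the global pain question of usual care. Appendix IV, the only pain form in the supplied text, reads "Please circle the intensity of your pain level at your" donor site, at this moment. It has no pre-operative version and no item for burn or overall pain. The chart-review list in Appendix III has no pain score at all.

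On the skin itself, I.A.1 says that "a graft is taken from a remote area of healthy skin, commonly the proximal thigh". II.D.1 requires "donor site anterior or lateral thigh", and II.D.2 excludes "burns to anterior thighs".

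The analysis in II.C.1 and V.A is a Student's t test for means and a chi-square test for categorical variables. No covariate, change score or other use of the baseline is described.

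**The concern.** A baseline pain score can show whether the arms were comparable at entry, and it can serve as a covariate that removes part of the between-patient variation in the outcome. It does neither if it hardly varies. A question about pain in skin that has not yet been cut is likely to be answered at the bottom of the scale by most subjects, and it says little about how strongly a given patient tends to report pain.

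The trial is small and its stated size leaves no spare power, so precision that could be had for almost no cost is worth having. A pre-operative score not collected in a useful form cannot be recovered later.

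**Working it through.** **Step 1: which site does the baseline refer to?**

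- For the donor site: II.E.3 mentions pre- and post-operative scoring and then describes a donor-site question; Appendix IV is worded only for the donor site.
- For another site, or none intended: II.B and II.E.2.a leave the site open. II.B uses donor-site wording only for the post-operative scores, and II.E.2.d places the donor-site assessment after surgery.

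The donor site is the more natural reading because no other form is supplied, but the text does not settle it.

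**Step 2: what follows from each reading?**

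- Donor site: the skin is healthy and remote from the burn (I.A.1) and anterior-thigh burns are excluded (II.D.2), so a floor is likely. Lateral-thigh burns are not named in the exclusions although the lateral thigh is an allowed donor site, so some non-zero scores are possible.
- Burn or overall pain: the score may well be informative, but the analysis does not use it.

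**Step 3: reproduce the plan's sample size.** Inputs from II.C: difference 2, SD 2.5, power 80%, significance level 0.05, 1:1 allocation. Two-sided testing is assumed, since the plan does not state it.

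n per group = 2 × (1.960 + 0.842)² × 2.5² / 2² = 2 × 7.85 × 1.5625 = 24.5, rounded up to 25.

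This matches II.C.3. Power at 25 per group is 80.7% by the normal approximation and 79.1% by the exact t test. No baseline score enters this calculation.

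**Step 4: effect of a flat baseline.** If every baseline is zero, a change score equals the post-operative score and its SD stays 2.5. As a covariate, a constant explains nothing. The planned comparison is unchanged.

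**Step 5: effect of an informative baseline.** With correlation r between the pre-operative score and post-operative donor-site pain, the residual SD is 2.5 × √(1 − r²). The documents give no value of r, so a range is assumed. Exact two-sided t test, 25 per arm:

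| r (assumed) | 1 − r² | Residual SD | Power |
|---|---|---|---|
| 0 | 1.00 | 2.500 | 79.1% |
| 0.1 | 0.99 | 2.487 | 79.5% |
| 0.2 | 0.96 | 2.449 | 80.7% |
| 0.3 | 0.91 | 2.385 | 82.8% |
| 0.5 | 0.75 | 2.165 | 89.3% |

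The covariate takes one degree of freedom (48 to 47), which changes each power figure by less than 0.1 percentage points.

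V.B gives a total of 40 patients where II.C.3 gives 50. At 20 per arm the figures are 69.3% at r = 0, 73.4% at 0.3 and 81.2% at 0.5. That conflict is a separate matter and is not caused by the pain form.

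**The case against.** The strongest reply is that nothing planned goes wrong. In a 1:1 randomised trial an unadjusted t test is unbiased without any baseline, and the sample size does not rest on one. That stands in full: this is a point about efficiency and clarity.

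A second reply is that no section says the baseline is recorded on the Appendix IV form. That also stands. Part of the document was not supplied, so another form cannot be ruled out. A reader might infer from Appendix IV that the baseline will be near zero for everyone. The documents do not support that: the site is not stated, no baseline values are given, and lateral-thigh burns are not excluded.

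A third reply is that pain from a burn may correlate only weakly with pain at a separate, freshly made and locally anaesthetised wound. This is fair. At r of 0.2 or below the gain is under 2 percentage points of power (80.7% − 79.1% = 1.6), and nothing in the documents shows that r is higher.

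What remains is that the plan collects a score from every subject without saying what it measures or what it is for.

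**Conclusion.** The point holds as a gap in specification with a possible loss of precision. The body site of the baseline is unstated, its use is unstated, and the supplied form and II.E.3 point to a site where a floor is likely before surgery.

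A reader might go further and infer that the comparison is biased or that the sample size is wrong. Neither follows: the planned test does not use the baseline, and 25 per group reproduces.

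The size ranges from nothing at r = 0 to about 10 percentage points of power at r = 0.5 (79.1% to 89.3% at 25 per arm). This rests on the plan's difference of 2 and SD of 2.5, two-sided testing, and an assumed correlation that the documents do not supply.

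**What to change.** - **Pre-operative form.** Make a pre-operative version of Appendix IV that asks for one defined measure, overall pain at this moment. Keep the donor-site wording for all post-operative forms. State in II.B and II.E.2.a that the baseline is overall pain.
- **Section V.A.** Replace the unadjusted t test for post-operative donor-site pain with a linear model containing treatment group and the pre-operative overall pain score, and report the adjusted difference with its 95% confidence interval. State which post-operative score the model is fitted to, because V.B expects a difference on days 1, 2 and 3 and names no single one as primary.

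The cost is one changed line on a one-minute scale that subjects already complete, plus one or two sentences of analysis text. The statistical cost is one degree of freedom, with little or no gain if the correlation turns out to be 0.2 or below.
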